# RECEIVING SPECIMENS/DATA FROM RESEARCH COLLABORATORS OUTSIDE PARTNERS

When specimens or data collected by research collaborators outside Partners will be sent to Partners investigators, indicate from where the specimens/data will be obtained and whether the specimens/data will contain identifiers that could be used by Partners investigators to link the specimens/data to individual subjects. When appropriate, submit documentation of IRB approval and a copy of the IRB-approved consent form from the institution where the specimens/data were collected.

Data derived from eternal collaborators on specimens curated as part of this study, specifically from the Broad Institute or other suppliers for analysis, will be shared as agreed upon in the contracts negotiated with Partners.

STATISTICAL ANALYSIS PLAN

Answer all questions accurately and completely in order to provide the PHRC with the relevant information to assess the risk-benefit ratio for the study. Do not leave sections blank.

PRINCIPAL/OVERALL INVESTIGATOR

[name] Research Staff, Diabetes Unit and Center for Genomic Medicine Richard B. Simches Research Center Massachusetts General Hospital (MGH) [name]

PROTOCOL TITLE

PREMIER: PREvention of Metabolic Illness through prEcision nutRition

FUNDING

Pilot and Feasibility Award program from the Nutrition Obesity Research Center at Harvard (NORCH)

VERSION DATE

04/22/2025

NCT ID number:

2019P002638

STATISTICAL ANALYSIS PLAN

Baseline characteristics will be reported as mean and standard deviation for continuous measures and number and percent for categorical variables. Characteristics will be reported stratified by genetic category (meal 1 and meal 2) and by meal selection (meal 2 only).

The primary exposures are genetic category (meal 1 and meal 2) and meal selection (meal 2). The co-primary outcomes are response profiles of insulin and glucose after meal 1 (0-180 minutes) and meal 2 (240-360 minutes). For each outcome, we will analyze the post-prandial response profile using linear mixed effects models adjusting for age, sex, BMI, three genetic principal components, and time, with a random effect for participant and a genetic category-by-time interaction to assess for between-group differences.

Secondary outcomes will include incremental area under the curve of insulin and glucose after each meal, meal selection, and lipid levels at 240 minutes after the first meal.

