Eligible participants who have reconsented to contact from the Partners HealthCare Biobank with desired genotypes and through Patient Research Invitation (PRI) will be contacted by study coordinators via our IRB approved contact letter.

Eligible participants will then be invited to attend the Translational and Clinical Research Center at MGH for their visit. Before the visit, participants will be sent pre-visit instructions, questionnaires and consent forms. Informed consent will be taken at the visit. After participants have given informed consent to take part they will have a fasting blood sample taken. In the event that a participant does not provide informed consent, no samples will be collected from the participants. Participants will then undergo a brief medical examination to measure BP, waist circumference, weight and height. During the clinical visit, participants will be cannulated, consume a set breakfast and an election lunch and provide blood samples at 9 time points (at baseline, [Breakfast meal], 30, 60, 120, 180, 240, [Lunch meal], 270, 300, 360 minutes (all minute intervals are relative to their first bite of the breakfast test meal)).

The subjects will also be asked to collect a stool sample the day of the visit or within 48 hours. In the event that a participant cannot produce a stool specimen during the visit, arrangements will be made to have the stool sample returned by mail. The participant will be given a stool collection kit containing illustrated instructions and all materials required to collect the stool specimen. The stool specimens will be collected into preservative-containing specimen tubes

using standard Human Microbiome Project protocols. There are no discernible risks associated with stool collection.

For studies involving treatment or diagnosis, provide information about standard of care at Partners (e.g., BWH, MGH) and indicate how the study procedures differ from standard care. Provide information on available alternative treatments, procedures, or methods of diagnosis.

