If a subject withdraws consent to the use of donated biological samples, any retained samples will be disposed of/destroyed. If these samples have already been used for data analysis (e.g. sequencing or metabolite measurement) it will not be possible to destroy this data and it will remain as a part of the study, but any data that is retained will be anonymized.

The Principal Investigator:

- Will ensure subjects' withdrawal of informed consent is recorded. Will ensure that biological samples from that subject, if stored at the study site, are immediately identified, disposed of/destroyed and the action documented.
- Will ensure that the laboratory(ies) holding the samples is/are informed about the withdrawn consent immediately and that samples are disposed of/destroyed and the action documented.

All participants must consume the baseline breakfast and provide baseline fasting bloods. Failure to meet these two requirements will result in termination of continued study participation as other endpoints will be unevaluable. If any other sample collections, dietary interventions, or blood timepoints are missed or unable to be completed, the subjects may continue with participation and these missing items will be logged by the study staff.

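### Meal selection is a self-chosen primary exposure, and the meal-2 model leaves it open to confounding by personal glycemic responsiveness: it has no meal-selection term and omits the breakfast response the trial already measures

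*SAP*

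**What the plan says.** The SAP names two primary exposures: "The primary exposures are genetic category (meal 1 and meal 2) and meal selection (meal 2"). The Protocol (Research Design and Methods) has participants "consume a set breakfast and an election lunch", so the second exposure is the participant's own choice. Neither document describes random allocation of lunch; the randomized study IDs are privacy codes. The SAP also lists meal selection among the secondary outcomes ("incremental area under the curve of insulin and glucose after each meal, meal selection, and lipid levels at 240 minutes after the first meal"), which treats it as behaviour and not as an assigned factor.

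On outcomes: "The co-primary outcomes are response profiles of insulin and glucose after meal 1 (0-180 minutes) and meal 2 (240-360 minutes"). On the model, to be used for each outcome: "linear mixed effects models adjusting for age, sex, BMI, three genetic principal components, and time, with a random effect for participant", together with "a genetic category-by-time interaction to assess for between-group differences". No meal-selection term, no meal-selection-by-time term and no measure of the breakfast response is listed.

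On the data available before lunch: "All participants must consume the baseline breakfast and provide baseline fasting bloods". Samples at 30, 60, 120 and 180 minutes follow breakfast and precede lunch. Other missed draws are logged and the participant continues.

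**The concern.** People who pick different lunches may already differ in how their glucose and insulin respond to food. The Protocol's aims make this plausible, because the study is meant to connect genetic influences on food preference with variable metabolic response. If preference and response share causes that the covariates do not capture, the meal-selection contrast mixes the effect of the lunch with the kind of person who chose it.

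The participant random effect does not deal with this. It accounts for repeated measures within a person and is assumed independent of the exposures. If responsiveness is related to choice, that assumption fails and the between-person difference goes into the meal-selection estimate.

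At stake is the reading of a primary contrast with 30 participants. The design offers a partial remedy that the SAP does not use: a same-day response to an identical meal, which the lunch cannot have influenced.

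**Working it through.** The documents give no power, effect size, SD, alpha or expected lunch split, so there is no plan figure to reproduce. The check is structural, followed by an illustration with assumed inputs.

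**Structural check.**
- Exposure of interest: meal selection, meal 2 only (SAP).
- Terms in the model: age, sex, BMI, three principal components, time, genetic category-by-time, participant random effect (SAP).
- Missing: meal selection, meal selection-by-time, and any measure of personal responsiveness.
- Available: breakfast glucose and insulin over 0-180 minutes, already a co-primary outcome. Its iAUC is already a secondary outcome.

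**Illustration, true meal-selection effect zero.** From the Protocol: n = 30. Assumed: responsiveness U is standard normal; each meal response is √r·U plus noise with total variance 1, so the two responses correlate at r; the log-odds of choosing one lunch are k·U; lunches split about evenly; two-sided alpha is 0.05.

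The mean gap in U between choosers is δ = 4∫u·φ(u)/(1+e^(−ku))du, which is 0.63 at k = 0.7 and 0.29 at k = 0.3. In large samples:
- without the breakfast response, bias = δ√r;
- with it, bias = δ√r(1−r)/(1−rδ²/4).

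At k = 0.7, r = 0.6: 0.63 × 0.775 = 0.49 SD without. With: 0.63 × 0.775 × 0.4 / (1 − 0.6 × 0.397/4) = 0.195/0.940 = 0.21 SD.

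False-positive rates come from simulated trials of 30, with genetic category (15/15) and six covariates in both models:

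| k | r | Bias without → with (SD) | False positives without → with |
|---|---|---|---|
| 0.7 | 0.4 | 0.40 → 0.25 | 14-15% → 9% |
| 0.7 | 0.6 | 0.49 → 0.21 | 20-21% → 8-9% |
| 0.7 | 0.8 | 0.56 → 0.12 | 26% → 7% |
| 0.3 | 0.4-0.8 | 0.19-0.26 → 0.11-0.05 | 7-10% → 5-6% |
| 0 | 0.4-0.8 | 0 → 0 | about 5% both |

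For scale, a 15/15 split has 80% power for (1.96 + 0.84) × √(2/15) = 1.02 SD. A bias of 0.49 SD is about half of that.

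**Random-effect check.** A random-intercept model on the 270, 300 and 360 minute rows used r = 0.5 and a correlation of 0.4 between U and the choice liability. The spurious effect was 0.46 SD without the breakfast response and 0.26 SD with it. The random effect alone did not remove it.

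**Precision when there is no confounding.** The large-sample SE ratio is √(1−r²): 0.92, 0.80 and 0.60 at r = 0.4, 0.6 and 0.8. With n = 30 and the covariates above, the SE fell from 0.43 to about 0.40, 0.35-0.36 and 0.27.

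**Cost of dropping incomplete breakfasts.** If 5% of draws are missed at each of four times (assumed), 1 − 0.95⁴ = 19% lack a complete iAUC, leaving about 24 of 30. A complete-case analysis at r = 0.4 then raises the SE from 0.43 to 0.49, which more than cancels the gain.

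**The case against.** **Genotype is already in the model.** A reader might infer that the SAP leaves out the very common cause the study proposes. It does not: genetic category-by-time is specified for each outcome. This stands. What remains unadjusted is responsiveness that genetic category does not explain, and the illustration was run with category included.

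**Confounding is not shown.** A reader might also infer that choice is confounded with responsiveness. The documents give no data on this; the aims only propose to look for such a link. This stands too. With k = 0 there is no bias, and with k = 0.3 the excess of false positives is small.

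**The illustration is not the planned test.** It uses one meal-2 response per person, and the mixed-model check omits the 240-minute row. Neither gives the error rate of a by-time test over 240-360 minutes. This is fair, and the figures should be read as showing the mechanism and its rough size. No closer match is possible while the meal-selection model is unwritten.

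**The change is not free.** Only breakfast and the fasting sample are mandatory, and a mixed model tolerates missing outcome rows where a fixed covariate does not. This stands and calls for a missing-timepoint rule.

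**A difference between choosers may be the target.** The study is a pilot that describes variability across groups and makes no causal claim about lunches. This has some force for wording. It does not rescue the contrast: with meal selection as a primary exposure for the meal-2 response, readers need to know whether a difference goes beyond what the same people already showed at breakfast.

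**Conclusion.** The point holds in a limited form. A self-selected primary exposure has no written model term, and the one model described omits the available measure of personal responsiveness. The contrast is open to confounding; the documents do not establish that it is confounded, or in which direction.

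If choice is moderately related to responsiveness, the size matters: about 0.4 to 0.6 SD of spurious effect and 15-26% false positives, falling to about 0.1 to 0.25 SD and 7-9% with the breakfast response. If the relation is weak, the rates are 7-10% and 5-6%. If there is none, the gain is precision only, provided participants are not dropped for missed draws. These figures rest on assumed correlations, choice slopes, an even lunch split and alpha 0.05.

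Adjustment does not make the contrast causal. One breakfast response is a noisy measure of responsiveness, and some bias remains in every confounded setting examined. The change is worth making in the SAP before the data are analysed.

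**What to change.** For the meal-selection contrast only, the SAP should:

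1. Write the model, with meal selection and meal selection-by-time as explicit terms, and keep the planned genetic category-by-time term.
2. Add the participant's own breakfast iAUC (0-180 minutes) of the same analyte, with its by-time term.
3. State how an incomplete breakfast curve is handled, either by computing the iAUC from the available timepoints or by imputing it, so that nobody is dropped for a missed breakfast draw.
4. Report the result as an association and name residual confounding as a limitation.

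The breakfast response should not be added to the genetic-category contrast, where it may itself be an effect of genotype and adjustment could remove part of what is being estimated.

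The cost is a short SAP addition, a few degrees of freedom and the missing-timepoint rule. No visit, sample or meal changes.

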#### **SPECIFIC AIMS**

Concisely state the objectives of the study and the hypothesis being tested.

The proposed study will examine interpersonal post-prandial responses to specific foods and meals based on personal features and characterize their variability across study groups. We propose to conduct a recall-by-genotype study among individuals with extremes genotypes influencing dietary intake from the Partners Healthcare Biobank to study the glycemic and metabolomic responses to a standardized and an election meal in a full-day clinic visit.

The specific objective of the PREMIER study is to carry out an interventional dietary study to measure the response of blood glucose and other biomarkers to a standardized meal or an election meal of varying nutritional content.

The specific hypothesis of this study is that deep molecular, physiological, and behavioral profiling can identify mechanisms underlying variable responses to specific foods and meals. The study will deliver preliminary data to link underlying genetic influences for food preferences with variable metabolic responses to different types of meals. If successful, it is foreseen that this data could be used to inform personalized dietary interventions focused on optimizing substrate metabolism and body weight.

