## **RESEARCH DESIGN AND METHODS**

Briefly describe study design and anticipated enrollment, i.e., number of subjects to be enrolled by researchers study-wide and by Partners researchers. Provide a brief summary of the eligibility criteria (for example, age range, gender, medical condition). Include any local site restrictions, for example, "Enrollment at Partners will be limited to adults although the sponsor's protocol is open to both children and adults."

We will recruit 30 healthy adults, 21-65 years of age for this study. Participants will be recruited from the Partners Healthcare Biobank, an electronic health records biorepository with clinical

and genetic data from  $\sim$ 36,000 individuals, who have consented to re-contact and through Patient Research Invitation (PRI). Participants will be excluded if they:

- Refuse or are unable to give informed consent to participate in the study.
- Have type I or type II diabetes mellitus or are taking medications for type II diabetes mellitus. Those not on medications but having a capillary glucose level of >126 mg/dL based on fingertip glucose measurements will be excluded.
- Are obese (BMI>30.0kg/m^2) or underweight (BMI $\leq 18.5$ kg/m^2).
- Have had a heart attack (myocardial infarction) or stroke in the last 3 years.
- Have had cancer in the last 3 years, excluding skin cancer.
- Have an ongoing inflammatory disease i.e. Rheumatoid arthritis, systemic lupus erythematosus, polymyalgia and other connective tissue diseases.
- History of cirrhosis and/or aspartate aminotransferase (AST) or alanine aminotransferase (ALT) more than 3 times the upper limit of normal (ULN).
- No known sickle cell disease or anemia.
- Are currently suffering from acute clinically diagnosed depression.
- Currently taking or intending to take during the study duration any medication known to affect glycemic parameters, such as glucocorticoids or fluoroquinolones.
- Are unable to fast from 9pm the night before the clinic visit until 9am on the clinic day
- Are pregnant or breastfeeding.
- Are participating in another clinical study.
- Are vegan, suffering from an eating disorder or unwilling to eat foods that are part of the study.

Briefly describe study procedures. Include any local site restrictions, for example, "Subjects enrolled at Partners will not participate in the pharmacokinetic portion of the study." Describe study endpoints.

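### Meal selection is declared a primary exposure for meal 2, but the only model stated for the co-primary outcomes has no meal-selection term

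*SAP*

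**What the plan says.** The SAP is about a page long. On exposures it states: "The primary exposures are genetic category (meal 1 and meal 2) and meal selection (meal 2". The co-primary outcomes are the insulin and glucose profiles over 0-180 minutes (meal 1) and 240-360 minutes (meal 2). One linear mixed model form is given for all of them. It adjusts for BMI, age, sex, time and three principal components of genotype, and it continues "with a random effect for participant and a genetic category-by-time interaction to assess for between-group differences".

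Meal selection appears in two other places in the SAP. One is the descriptive table: "Characteristics will be reported stratified by genetic category (meal 1 and meal 2) and by meal selection (meal 2 only". The other is the list of secondary outcomes: "Secondary outcomes will include incremental area under the curve of insulin and glucose after each meal, meal selection, and lipid levels". Neither comes with an inferential method.

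The Protocol (Research Design and Methods) has participants "consume a set breakfast and an election lunch and provide blood samples at 9 time points", with post-baseline samples at "30, 60, 120, 180, 240, [Lunch meal], 270, 300, 360 minutes". On size it says: "We will recruit 30 healthy adults, 21-65 years of age for this study". It contains no statistical model.

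**The concern.** A model can estimate only the terms that are in it. The group contrast in the stated model belongs to genetic category, so fitting it to the meal 2 profiles says nothing about how those profiles differ between lunches. A declared primary exposure would then end the study with no primary result.

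If the gap is found after the data are in, the meal-selection model will have to be written with the profiles already visible. One decision would matter in particular: whether meal selection joins genetic category in the model or replaces it. The two can give different answers when genotype is related to both choice and response. A line in the SAP now removes that freedom.

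**Working it through.** The documents state no power, alpha, SD or effect size, so there is no figure to reproduce. The check is a reading of terms, followed by arithmetic on the cost of adding the missing ones.

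**1. Where each exposure is used**

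| Use in the SAP | Genetic category | Meal selection |
|---|---|---|
| Named as primary exposure | meals 1 and 2 | meal 2 |
| Stratifies the baseline table | yes | yes |
| Term in the model for the profiles | by-time interaction | none |
| Listed as secondary outcome | no | yes, no method given |

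**2. Parameter count for meal 2**

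The time points 240, 270, 300 and 360 minutes and N = 30 come from the Protocol. Categorical time, two genetic categories and two lunches are assumptions.

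- Stated model: intercept 1 + covariates and components 6 + time 3 + genetic category 1 + genetic category-by-time 3 = 14. None of these carries meal selection.
- Added terms: meal selection 1 + meal selection-by-time 3 = 4, giving 18.
- A design matrix built for 30 participants at four times has full rank at 18 columns, so the added terms are estimable.

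**3. Power of the meal selection-by-time test (illustrative)**

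Assumptions for glucose: the SD of the 240-to-300 minute change is 25 mg/dL, so the within-participant residual variance is 25²/2 = 312.5. The lunch difference is 0, d/2, d and d/2 at the four times. All 30 participants are evaluable, and the test is at 5%.

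- The mean of the four differences is d/2, so the sum of squared deviations is d²/2. For d = 20 this is 200.
- Noncentrality = N p(1−p)(1−φ²) × 200 / 312.5. Here p is the share choosing one lunch and φ is the correlation between genotype and choice.
- Denominator df with genetic category kept: 120 − 30 − 3 − 3 − 3 = 81. Numerator df is 3.

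| d = 20 mg/dL | Noncentrality | Power |
|---|---|---|
| 15/15, φ = 0 | 7.5 × 1 × 0.64 = 4.80 | 41% |
| 15/15, φ = 0.4 | 7.5 × 0.84 × 0.64 = 4.03 | 35% |
| 15/15, φ = 0.6 | 7.5 × 0.64 × 0.64 = 3.07 | 27% |
| 6/24, φ = 0 | 4.8 × 1 × 0.64 = 3.07 | 27% |
| 3/27, φ = 0 | 2.7 × 1 × 0.64 = 1.73 | 16% |

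At φ = 0, the d detectable with 80% power is 31, 39 and 51 mg/dL for splits of 15/15, 6/24 and 3/27.

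**4. Why genetic category should stay in the added model**

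With 15 per genotype group, the average bias from leaving genetic category out is the direct genotype effect times the difference between the groups in the share choosing a given lunch. Take a true lunch difference of 20 mg/dL and an assumed direct genotype effect of 20 mg/dL.

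- Choice 60/40: 20 + 20 × 0.2 = 24
- Choice 70/30: 20 + 20 × 0.4 = 28
- Choice 80/20: 20 + 20 × 0.6 = 32

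With genetic category and its time interaction in the model, simulation gave 20 in each case. If genotype has no effect on response, the two models agree on average.

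**The case against.** The strongest reply is that this is an omission in a one-paragraph summary. The SAP speaks of models in the plural, mentions between-group differences shortly after naming both exposures, and does not list a genetic-category main effect either, although one is plainly implied. On that reading, lunch groups were meant to be handled in the same way. The plan does not say so, however: the phrase about group differences is attached to genetic category-by-time. Granting the intention also leaves open whether meal selection replaces genetic category or joins it.

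Two stronger readings are tempting, and the documents do not support them.

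- A reader might infer that a study aim goes unanswered. The aim in the Protocol is genetic: "The study will deliver preliminary data to link underlying genetic influences for food preferences with variable metabolic responses to different types of meals". The genotype-by-time model, together with meal selection as a secondary outcome, bears on that aim. The firm ground is the SAP's own label of primary exposure.
- A reader might take the shift from 20 to 32 mg/dL as the size of the defect. It measures the harm of removing genetic category, which the stated model already contains, and it is driven by the assumed genotype effect. In simulations with no lunch effect and a genotype effect of 20 mg/dL, the 5% test without genetic category rejected about 10% of the time at 70/30 and 17% at 80/20. Halving the genotype effect to 10 brought these to about 6% and 7%.

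It also stands that this is a 30-person pilot with modest power for the added test, and that the test adds one formal comparison for each of two outcomes.

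**Conclusion.** The omission is certain, because it follows from the text alone: as written, the plan gives no estimate or test of a declared primary exposure on the meal 2 insulin and glucose profiles. Its reach is limited to that exposure at meal 2. The omission does not affect the genotype comparisons at either meal. It should be corrected before analysis, but it does not undermine the study.

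The power figures show only what the correction can deliver. The SD, effect shape, lunch split, number of lunches and genotype-choice correlation are all assumed. The bias figures support one narrow conclusion, that genetic category belongs in the added model.

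**What to change.** For the meal 2 (240-360 minute) insulin and glucose profiles:

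- Keep the existing model as the genotype analysis.
- Add a second model with every term of the stated one, including genetic category and its interaction with time, plus meal selection and meal selection-by-time. Test meal selection-by-time.
- Report the result as an association, because participants choose their own lunch.

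Leave meal 1 unchanged. If no inferential analysis of lunch choice is intended, stop calling meal selection a primary exposure; either course resolves the inconsistency.

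The cost is SAP wording, with no extra participants, samples or procedures. With two lunches and categorical time the second model has 4 more parameters; three lunches would add 2 main effects and 6 interactions. Power depends on a lunch split that the study does not control, and it falls further if choice follows genotype. The meal-selection result should be presented with that limitation stated.

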#### **EXPECTED BENEFITS**

Describe both the expected benefits to individual subjects participating in the research and the importance of the knowledge that may reasonably be expected to result from the study. Provide a brief, realistic summary of potential benefits to subjects, for example, "It is hoped that the treatment will result in a partial reduction in tumor size in at least 25% of the enrolled subjects." Indicate how the results of the study will benefit future patients with the disease/condition being studied and/or society, e.g., through increased knowledge of human physiology or behavior, improved safety, or technological advances.

There is no specific individual health benefit expected as a direct result of participating in this study. However, participants will be provided information about the laboratory results of their individual participation in the research study. We will provide lab results from the visit day that include glucose and insulin levels, kidney and liver function test, and lipid panel results that we will measure. The research we are doing is only a stepping stone in understanding metabolic responses to foods. Most of the findings that come from the study will not be relevant to personal health. These studies will help advance our clinical and scientific understanding of how metabolic processes in the body are influenced by diet and our microbiome and ultimately how these processes may contribute to factors influencing human health and disease.

Participants will be remunerated for their time (US \$70) following successful completion of the study. The remuneration will be in the form of general use, credit-card style (e.g. American Express or Visa) pre-loaded gift cards. Participants will receive two free meals during the study visit. They will also receive a voucher for your transportation to the study visit, which will cover the cost of parking or 2 passes on the MBTA.

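### The lipid secondary outcome is a 240-minute level with no fasting reference, so it cannot by itself be read as a response to breakfast

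*SAP*

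**What the plan says.** The SAP's secondary outcomes include "meal selection, and lipid levels at 240 minutes after the first meal". In the same sentence the glucose and insulin outcomes are "incremental area under the curve of insulin and glucose after each meal", which are referenced to a starting value by construction. The SAP describes one model, a linear mixed model for the post-prandial profile. It adjusts for age, sex, BMI, three genetic principal components and time, and includes a genetic category-by-time interaction. It has no term for the fasting value of an analyte, and the SAP gives no model or contrast for the single lipid time point.

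The Protocol, Specific Aims, states the objective as to "measure the response of blood glucose and other biomarkers to a standardized meal or an election meal of varying nutritional content" and describes the design as a "recall-by-genotype study among individuals with extremes genotypes influencing dietary intake".

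Under Research Design and Methods, the planned enrolment is "We will recruit 30 healthy adults, 21-65 years of age for this study" and the draws are "at baseline, [Breakfast meal], 30, 60, 120, 180, 240, [Lunch meal], 270, 300, 360 minutes". On required samples, the protocol says: "All participants must consume the baseline breakfast and provide baseline fasting bloods". Under Expected Benefits it says: "We will provide lab results from the visit day that include glucose and insulin levels, kidney and liver function test, and lipid panel results". The lipid fractions are not named, and neither is the draw on which the panel is run.

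**The concern.** The co-primary outcomes are profiles over time and the other biomarker secondary outcomes are increments. Only lipids are given as a raw level. In a randomized comparison that would matter little, because fasting values would be balanced in expectation. Here the categories are formed by genotype, so equal fasting lipids cannot be assumed.

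If the 240-minute comparison is reported as evidence on response to breakfast, two errors are possible. A fasting difference could pass for a difference in response, or it could offset a real one. Leaving the reference unstated also leaves room to choose, after the data are seen, among raw level, change and fasting-adjusted value, which can give different answers.

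**Working it through.** **No figure to reproduce.** The documents give no lipid SD, fasting difference, correlation, group split, significance level or power. The target follows from algebra. The sizes below are illustrations under stated assumptions.

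**What each analysis estimates.** Let b be the fasting difference between genetic categories, d the difference in response to breakfast, and r the within-group correlation between fasting and 240-minute values, with equal SDs.

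- Raw 240-minute level: b + d.
- Change from fasting: d, if the response does not scale with the fasting level. If each group's mean response also rises by k per unit of its mean fasting level, change estimates d + k·b.
- 240-minute value adjusted for fasting: d + b(1 − r).

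With b = 0.5 SD and d = 0, the raw level estimates 0.50 SD and change estimates 0. The adjusted value estimates 0.5 × (1 − r) = 0.35, 0.25, 0.15 and 0.10 SD at r = 0.3, 0.5, 0.7 and 0.8.

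**Assumptions for the sizes.** 15 per group, equal SDs, two-sided 0.05, additive response, and six covariates unrelated to the outcome (age, sex, BMI and three principal components). Carrying these covariates over from the profile model is an extrapolation.

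**Share of studies with p<0.05 when the response is identical (d = 0).** Simulation, 20,000 runs per case:

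| Fasting difference | Raw level | Adjusted for fasting, r = 0.3 / 0.5 / 0.7 / 0.8 | Change |
|---|---|---|---|
| 0 | 5% | 5% at each r | 5% |
| 0.25 SD | 9% | 6.8% / 6.2% / 5.4% / 5.5% | 5% |
| 0.5 SD | 21–22% | 12.7% / 9.7% / 7.6% / 6.4% | 5% |

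**Masking, chosen as exact cancellation (b = −0.5 SD, d = +0.5 SD).** The raw level estimates 0 and gives p<0.05 in about 5%. Change estimates 0.50 SD, with p<0.05 in about 16%, 21%, 33% and 46% at r = 0.3, 0.5, 0.7 and 0.8. The adjusted value estimates 0.5 − 0.5(1 − r) = 0.15, 0.25, 0.35 and 0.40 SD.

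**Precision.** The difference detectable with 80% power comes from the noncentral t distribution. The standard error is √[F × (1/15 + 1/15)] SD. F is the outcome's relative variance times the expected cost of p covariates, 1 + p/(n − p − 3), with n = 30.

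- Raw: p = 6, df = 22, F = 1 + 6/21 = 1.286, giving 1.21 SD.
- Change: p = 6, df = 22, F = 2(1 − r) × 1.286, giving 1.44, 1.21, 0.94 and 0.77 SD at the four r values.
- Adjusted for fasting: p = 7, df = 21, F = (1 − r²) × (1 + 7/20) = (1 − r²) × 1.35, giving 1.19, 1.08, 0.89 and 0.75 SD.

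Change equals the raw level in precision where 2(1 − r) = 1, that is r = 0.5, and is worse below that. A 10/20 split gives 1.29 SD for the raw level and 1.52 SD for change at r = 0.3. Without covariates the raw figure at 15/15 is 1.06 SD.

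**Feasibility.** The fasting draw is required for continued participation. The 240-minute draw is listed before lunch, so the interval between the two contains breakfast only.

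**The case against.** The strongest reply is that the SAP wording is not wrong. Read literally it specifies a level. The authors wrote an increment for glucose and insulin in the same sentence and may have chosen a level for lipids deliberately. The total difference at 240 minutes is a legitimate quantity. This stands: what the documents do not support is reading that level as a meal response.

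A reader might go further and infer that the lipid result will be biased. That does not follow. Bias would require that lipids are compared by genetic category, that the result is read as a response, and that fasting lipids differ between categories. The first is an inference from genetic category being the primary exposure for the first meal, and no document reports or predicts the third. The genotypes were selected for their influence on dietary intake.

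A reader might also infer that change must replace the raw level and rank above fasting adjustment. The documents do not settle that. Change is free of the fasting difference only under a response that does not scale with the fasting level, which is exactly what the simulation assumed. Fasting adjustment has the smallest detectable difference at every r considered. With equal fasting lipids and a true response difference of 0.5 SD, change would give p<0.05 in about 16% of studies at r = 0.3, against about 21% for the raw level.

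**Conclusion.** The concern holds in a limited form. As specified, the lipid outcome has no fasting reference. In a comparison of genotype groups it would estimate fasting difference plus breakfast response, so alone it does not address the stated aim of measuring response to a meal. This conclusion about the target needs no numerical assumption beyond the comparison being by genetic category.

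The size is unknown. Under the assumptions above, a fasting difference of 0.25 SD raises the share of raw-level comparisons with p<0.05 from 5% to about 9%, and one of 0.5 SD raises it to about 22%, with no difference in response. With equal fasting lipids the effect is nil. The case rests on what is estimated, not on precision.

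Severity is minor: this is one secondary outcome of a 30-person pilot, and no primary conclusion depends on it.

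**What to change.** In the SAP:

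1. Name the lipids, and state that the same ones are measured in the mandatory fasting sample and the pre-lunch 240-minute sample.
2. Add a fasting-referenced analysis by genetic category: a linear model with age, sex, BMI and the three genetic principal components.
3. Report both the change from fasting and the 240-minute value adjusted for fasting. Note that in non-randomized groups the adjusted estimate keeps about (1 − r) of any fasting difference, and that change is free of it only if the response does not scale with the fasting level.
4. If the raw 240-minute level is kept, interpret it as the total difference between categories, not as a meal response.

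The cost is a few lines of text and one small additional analysis. If the lipid panel is not already run on both samples, one more assay is needed on blood already drawn. Change loses precision against the raw level when r is below 0.5; in the illustration at r = 0.3 the detectable difference is 1.44 against 1.21 SD.
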